Subjects will be randomized into two arms, the HPI arm and the non-HPI arm. The randomization will be done automatically by the Electronic Data Capture (EDC) system. The subject will be blinded. Due to the nature of the interventions, the investigators and treating anesthesiologist, anesthesia nurse, intensivist and critical care nurse will not be masked to group allocation.

The HPI arm will utilize the HemoSphere Advanced Monitoring Platform with the Acumen™ HPI Software Feature. The treating cardiac anesthesiologist/anesthesia nurse in the operating room and the critical care

THIS DOCUMENT CONTAINS CONFIDENTIAL AND PROPRIETARY INFORMATION OF EDWARDS LIFESCIENCES, LLC. IT MAY NOT BE REPRODUCED OR DISCLOSED WITHOUT PRIOR WRITTEN PERMISSION FROM EDWARDS LIFESCIENCES, LLC.

Edwards Lifesciences, Edwards, the stylized E logo, HemoSphere, Acumen IQ, Swan Ganz and ForeSight Elite are trademarks of Edwards Lifesciences Corporation.

nurses/intensivists/advance practice providers in the ICU will be trained to understand Acumen™ HPI Software Feature and the advanced hemodynamic parameters provided. The treating anesthesiologist, anesthesia nurse, intensivist, and critical care nurse will be provided with guidance by means of a flowchart suggesting what to treat and what the cause of hypotension is (see Figure 3. HPI Arm Protocol). Timing of treatment and choice of treatment is then left to the discretion of the attending intensivist and critical care nurse.

In the non-HPI arm, clinicians will be using non-protocolized standard of care to treat subjects.

[figure not shown]

Figure 3. HPI Arm Protocol

Note: Clinicians should validate the appropriateness of protocol recommendations, and provide treatment based upon their clinical judgment.

Schema

Screening and consenting subjects will occur during the pre-anesthesia visit. Once the subject is consented, the subject will undergo a Mini-Mental State Examination (MMSE).

After the subject has consented and prior to surgery, the subject will be randomized into the HPI arm or the non-HPI arm (control group). The randomization assignment must not be revealed to the clinicians until surgery. If a clinician randomizes the subject, they must not be involved in the care of the subject in the OR. A clinical research coordinator or a designee who is delegated to consent and/or randomize the

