THIS DOCUMENT CONTAINS CONFIDENTIAL AND PROPRIETARY INFORMATION OF EDWARDS LIFESCIENCES, LLC. IT MAY NOT BE REPRODUCED OR DISCLOSED WITHOUT PRIOR WRITTEN PERMISSION FROM EDWARDS LIFESCIENCES, LLC.

Edwards Lifesciences, Edwards, the stylized E logo, HemoSphere, Acumen IQ, Swan Ganz and ForeSight Elite are trademarks of Edwards Lifesciences Corporation.

5. Subjects with pre-op or pre-pump or post-pump LVEF <15%¹
6. Subjects requiring heart transplant
7. Subjects with pre-existing circulatory support devices or planned circulatory support devices post-bypass
8. Subjects requiring emergency surgery
9. Subjects with known or identified severe PAH (defined as pulmonary systolic pressures > 70mmHg or mean pressures > 55mmHg) as determined by a pre-operative echo or intraoperative Swan-Ganz²
10. Subjects with cardiovascular instability in the operating room necessitating the need to go back on bypass for a subsequent run

¹ Pre-operative echo will take precedence over pre-pump echo. In the event of discrepancy on numbers, a final decision will be made based on a discussion between the PI and the cardiac anesthesiologist performing the pre-pump echo.

² Severe PAH is qualified as PA systolic pressure >70mmHg and/or mean pressure >55mmHg as documented on a pre-operative echo or cardiac catheterization. Or in the absence of these a sustained pressure as above after the insertion of a Swan-Ganz for at least 60 minutes in the pre-bypass period. All severe PAH pressure values should be attributed to an irreversible etiology in the best clinical judgement of the treating team to meet exclusion criteria.

THIS DOCUMENT CONTAINS CONFIDENTIAL AND PROPRIETARY INFORMATION OF EDWARDS LIFESCIENCES, LLC. IT MAY NOT BE REPRODUCED OR DISCLOSED WITHOUT PRIOR WRITTEN PERMISSION FROM EDWARDS LIFESCIENCES, LLC.

Edwards Lifesciences, Edwards, the stylized E logo, HemoSphere, Acumen IQ, Swan Ganz and ForeSight Elite are trademarks of Edwards Lifesciences Corporation.

HPI CARE Trial
Protocol #: 2020-19

Screen Failures [or Late Screen Failures]

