2.2. Overall Study Design

This study is a single-center randomized controlled trial to determine whether use of the Acumen HPI Software Feature to guide hemodynamic management in cardiac surgery post-CPB and up to 8-hours post-CPB reduces the amount of hypotension (defined as MAP < 65 mmHg). The results of the HPI arm will be compared with a control group (non-HPI arm). In the control group, the clinician will use non-protocolized standard of care management per clinician and provider judgement.

In accordance with 21 CFR 812.3(m), this trial does not meet the definition of a significant risk investigation for the following reasons:

- The devices in the HPI arm are being studied in accordance with the indications for use and intended use granted by FDA in DEN160044 (March 16, 2018), and therefore are not investigational devices.
- The devices in the treatment group are not implants.

 Edwards	Revision Date: May 7, 2024	Rev	For Use Only by Affiliates of Edwards Lifesciences	Page 6
	Title	A randomized trial of the Hypotension Prediction Index in the cardiac operating room and the intensive care unit		

- The devices in the treatment group do not present a potential for serious risk to the health, safety, or welfare of a subject as only subjects requiring an arterial line will be eligible for enrollment in the trial and the trial relies on the intervention of a learned intermediary prior to initiation of treatment. The devices in the treatment group are of substantial importance in diagnosing, mitigating, or treating disease, or otherwise preventing impairment of human health; however, as described in the de novo classification letter for DEN160044 (March 16, 2018), the Class II (special) controls provide a reasonable assurance of the safety and effectiveness of adjunctive predictive cardiovascular indicators, and specifically, the Acumen™ HPI Software Feature, met the special controls as established by FDA; and the devices in the treatment group are not of substantial importance in curing disease.

Subject participation will include preoperative trial eligibility screening and consent, planned surgical intervention, post-intervention follow-up through discharge, and 30 days post procedure. Discontinued subject data will be analyzed under intent-to-treat and data will be used for safety and performance analyses.

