2.3. Study Subject Randomization Schema

Subjects will be randomized into two arms, the HPI arm and the non-HPI arm. The randomization will be done automatically by the Electronic Data Capture (EDC) system. To keep the subject balance between HPI arm and control group (1:1), sequentially, 2, or 4, or 6 study subjects passed the qualification screening with yes for all inclusion criteria and no for all exclusion criteria, signed the IFC form, assigned the subject ID, form a subject block. The randomization allocation of study subject will conduct within each block depending on the random number generated from uniform distribution, the block specified cutoff probability will be selected to guarantee half of the subjects will go to the control group and another half will be assigned to the HPI arm. The probability cutoff point to assign a subject to HPI arm or control group will variate among blocks, which is determined by the random seed and the uniform random number produced for each study subject.

Due to system limitations with the electronic data capture (EDC) system, there is a manual process for handling screen failures who are randomized (late screen failures). There is a small chance that some randomization assignments will be skipped due to these screen failures (partially filled blocks), or some randomization assignments given out more than once. These issues may introduce bias in the study. Should these events occur, an additional sensitivity analysis will take place. If randomization assignments are skipped, the study will be assessed to ensure a reasonable balance exists between the cohorts. The collected baseline variables will be compared to ensure that both cohorts are well matched.

 Edwards	Revision Date: May 7, 2024	Rev	For Use Only by Affiliates of Edwards Lifesciences	Page 7
	Title	A randomized trial of the Hypotension Prediction Index in the cardiac operating room and the intensive care unit		

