4.1. Modified ITT (mITT) Population

The mITT population is composed of all subjects who pass the screen (inclusion/exclusion) evaluation, sign the informed consent form (ICF), are assigned a subject ID, and are randomized to a study group, an arterial line has been placed and the FloTrac or Acumen IQ Sensor has been connected.

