4.2. Full Analysis Set (FAS) Population

The FAS population is a subset of the mITT population and will consist of all enrolled pivotal subjects who undergo cardiac surgery ≥ 2 hours duration with the aid of cardiopulmonary bypass, have one postoperative assessment, and have valid hemodynamic observations.

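### The primary analysis set depends on events after randomisation, and the plan does not settle whether subjects who meet a late exclusion also leave the safety set

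*Combined protocol and SAP*

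**What the plan says.** Protocol section 4 (Schema) fixes the timing: "After the subject has consented and prior to surgery, the subject will be randomized into the HPI arm or the non-HPI arm (control group"). Section 6 (Procedure) places randomisation on the day of the procedure. Treating clinicians in the OR and ICU are not masked (section 4, Randomization and Blinding).

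Three exclusion criteria in protocol section 5 can be met after that point:
- Exclusion 10: "Subjects with cardiovascular instability in the operating room necessitating the need to go back on bypass for a subsequent run".
- Exclusion 5, which begins "Subjects with pre-op or pre-pump or post-pump LVEF" and has a 15% cut-off. Its post-pump part needs a completed bypass run.
- Exclusion 9, where severe PAH may be identified by an intraoperative Swan-Ganz. Footnote 2 confines this to the pre-bypass period.

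SAP 4.1 builds the mITT from "all subjects who pass the screen (inclusion/exclusion) evaluation, sign the informed consent form (ICF"), with randomisation and sensor connection also required. SAP 4.2 makes the FAS a subset of the mITT and adds that subjects must undergo on-pump surgery lasting 2 hours or more, and must "have one postoperative assessment, and have valid hemodynamic observations". The primary endpoint is analysed on the FAS (SAP 8.1) and the safety endpoint on the mITT (SAP 8.2).

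SAP 2.3 expects some randomised subjects to fail screening late: "there is a manual process for handling screen failures who are randomized (late screen failures"). Against this, SAP 2.2 and protocol section 4 both state: "Discontinued subject data will be analyzed under intent-to-treat".

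**The concern.** Instability after bypass may be an outcome of the care being compared. Protocol section 8 lists heart failure and profound hypotension among the risks of under- or overtreatment under the HPI protocol. If subjects leave the primary set because they became unstable, had a short operation or died before a postoperative assessment, the arms compared are no longer the arms randomised. The treating team, which knows the allocation, also has a part in whether some of these conditions are met.

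If late exclusions are handled as screen failures, protocol section 5 (Screen Failures) requires only demography, failure details and eligibility data. The data needed to restore these subjects later might then not exist.

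**Working it through.** **1. Which conditions follow randomisation?**
- Surgery of at least 2 hours, a postoperative assessment and valid hemodynamic data (SAP 4.2): all three. This does not depend on how the mITT is read.
- Exclusion 10 and post-pump LVEF: always after randomisation. Study care may affect them, but this is not certain. The OR endpoint period opens around protamine (protocol section 3), and a return to bypass or a post-pump echo could come earlier.
- Intraoperative PAH: after randomisation but before bypass, so post-bypass HPI care cannot cause it.

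**2. Does meeting a late exclusion remove a subject from the mITT?**
- For removal: the mITT requires passing the inclusion/exclusion evaluation, and SAP 2.3 recognises randomised screen failures.
- Against removal: the schedule of events puts that evaluation in the screening column only; SAP 2.3 describes all exclusions as cleared before allocation (impossible for exclusion 10); SAP 4.6 extends screen failure only to unmet inclusion criteria; and the intent-to-treat sentence points the other way.
- The SAP's precedence clause (section 1) cannot settle this, because the SAP contains both the intent-to-treat sentence and the restrictive sets.

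**3. Does a planned sensitivity analysis restore these subjects?** Not clearly. SAP 8.1.3 item B2 compares an all-subject analysis with the FAS, but ties it to missing covariate information or cohort structure.

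**4. The plan's own figures reproduce.** Inputs from SAP 2.4.3: means 29 and 20.3 min (difference 8.7), SDs 29.49 and 22.33, one-sided alpha 0.025, power 0.80.
- Common SD = sqrt((29.49² + 22.33²)/2) = 26.16.
- n = 2 × (1.960 + 0.842)² × 26.16² / 8.7² = 142 per arm, as stated.
- 142 × 1.12 × 1.10 = 174.9, matching the final 175 (SAP 8.1.4).

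**5. Size of the bias with no true effect.** Assumptions, none from the documents: a share f of an arm is removed, and those subjects average M hypotensive minutes in either arm. The mean over all randomised subjects is 29 min in both arms.
- Retained mean = (29 − f × M)/(1 − f). Bias = HPI retained mean − control retained mean.
- Equal f and equal M: bias 0.
- f = 2% control, 4% HPI, M = 60: 26.6/0.96 − 27.8/0.98 = 27.71 − 28.37 = −0.66 min (7.6% of 8.7).
- M = 90: 25.4/0.96 − 27.2/0.98 = 26.46 − 27.76 = −1.30 min (14.9%).
- M = 120: 24.2/0.96 − 26.6/0.98 = 25.21 − 27.14 = −1.93 min (22.2%).
- f = 4% control, 2% HPI: +0.66, +1.30 and +1.93 min, against HPI.

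**6. Effect on the test.** With 171.5 and 168 subjects retained of 175 per arm, SE = 29.49 × sqrt(1/171.5 + 1/168) = 3.20. One-look type I error at the 0.0154 level = Φ(−bias/SE − 2.160). For 2% control and 4% HPI this gives 0.025, 0.040 and 0.060 at M = 60, 90 and 120. With the shares reversed it gives 0.009, 0.005 and 0.003.

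**7. Loss of numbers alone.** At 175 per arm and alpha 0.0154, one-look power is 82.9%. With 2%, 5% or 10% removed equally it is 82.1%, 80.9% or 78.6%. Selection is the issue more than sample size.

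**The case against.** The strongest reply is that no sentence says a subject who returns to bypass is dropped. If the inclusion/exclusion evaluation means the preoperative screen, later instability removes no one from the mITT, and the intent-to-treat sentence fits that reading. Subjects whose procedure is aborted after exposure are also followed for 30 days (protocol section 5, Early Withdrawal). This stands. A reader might infer that the safety comparison certainly loses its worst cases, and the documents do not support that.

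Two related inferences also fail. A death before any postoperative assessment leaves the FAS, but that condition is not in the mITT, on which deaths are summarised (SAP 9.1). Nor is each late exclusion necessarily a lost serious event, because the SAE definition does not name a return to bypass.

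The reply does not rescue the primary analysis. The 2-hour, postoperative-assessment and valid-data conditions remain in the FAS whichever reading of the mITT is right.

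It is also fair to say that simply adding subjects back is not enough. The endpoint is total minutes, so a subject who dies early would score a short, favourable duration unless a rule prevents it.

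**Conclusion.** The primary comparison is conditioned on post-randomisation events; this follows directly from SAP 4.2 and 8.1. For safety, the mITT, screen-failure and intent-to-treat passages conflict and must be reconciled.

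The size and direction of any bias are unknown. The range of −0.7 to −1.9 min (8% to 22% of the planned effect) rests on assumed removal of 2% of control and 4% of HPI subjects averaging 60 to 120 min. It is zero under the null with equal rates and severity, and reverses sign if control loses more. A reader might infer a bias in favour of HPI, but the documents give no rates, severity or arm difference to support one. This is a cheap improvement that closes an avoidable route to bias.

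**What to change.** In SAP 4.1, 4.2, 8.1 and 8.2:
- Define the safety set as all randomised pivotal subjects with the sensor connected, analysed as randomised.
- Define the primary set as those subjects with any valid MAP data in the endpoint window, analysed as randomised. Drop the 2-hour, postoperative-assessment and post-randomisation exclusion conditions.
- Reconcile the mITT, screen-failure and intent-to-treat passages so that meeting exclusion 5, 9 or 10 after randomisation does not remove a subject from analysis. Eligibility criteria and clinical care need not change.
- Prespecify return to bypass and early death as intercurrent events. Keep post-protamine, off-bypass minutes that precede any second run, and do not let early death count as a favourable short duration.
- Report late exclusions, and subjects without valid MAP, by arm with reasons.
- Keep the current FAS as a sensitivity analysis.

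No new patients are needed. The costs are slightly more variance, an intercurrent-event rule to write, and full data collection for late exclusions in place of the minimal screen-failure record.

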6. SCHEDULE OF EVENTS & PROCEDURES

Schedule of Events

Study Procedure / Exam	Subject Screening	Procedure	Day 1 Post-Op	Day 2-7 Post-Op	Discharge	30-Day Follow Up (±15 Days)
Obtain Informed Consent	X					
Perform Inclusion / Exclusion Evaluation	X					
Obtain Medical History / Subject Demographics ¹	X					
MMSE	X		X	X ²		X ³
Assign Subject ID		X				
Randomize Subject		X				
Enter Subject Data into Monitor		X				
Vital Signs		X				
NT pro-BNP		X	x	X ⁴		
Troponin		X	X	X ⁴		
Creatinine		X	X	X ⁵		
ABG Labs		X				
Basic Labs		X				
Monitoring Duration		X				
Data download from Monitor		X				
Obtain Fluid and Vasoactive Medication Administration Record ⁶		X	X			
CAM			X ⁷	X ⁸		
Complete eCRFs	X	X	X	X	X	X

¹ Medical History / Subject Demographics / Surgical and Clinician Demographics can be obtained prior to procedure, either at the screening visit or on the day of procedure.

² MMSE will likely take place between Day 2-7 Post-Op, but this may vary.

³ Only required for patients who will be returning to Wake Forest Baptist Medical Center for 30-day follow up

⁴ Troponin and NT Pro-BNP to be drawn on POD 1, 2 and 3

⁵ Creatinine to be collected on POD 1, 2 and 3

⁶ Can be collected via the hospital record system anytime on the day of procedure or thereafter.

⁷ CAM will be administered twice during post-op Day 1. While in the ICU, CAM-ICU 7 will be utilized. Once the subject is transferred to the hospital floor, bCAM will be utilized.

⁸ CAM will be administered twice per day until Day 7 Post-Op or until the subject is discharged (whichever occurs first). While in the ICU, CAM-ICU 7 will be utilized. Once the subject is transferred to the hospital floor, bCAM will be utilized.

THIS DOCUMENT CONTAINS CONFIDENTIAL AND PROPRIETARY INFORMATION OF EDWARDS LIFESCIENCES, LLC. IT MAY NOT BE REPRODUCED OR DISCLOSED WITHOUT PRIOR WRITTEN PERMISSION FROM EDWARDS LIFESCIENCES, LLC.

Edwards Lifesciences, Edwards, the stylized E logo, HemoSphere, Acumen IQ, Swan Ganz and ForeSight Elite are trademarks of Edwards Lifesciences Corporation.

HPI CARE Trial
Protocol #: 2020-19

Record Adverse Events, if applicable		X	X	X	X	X
30-day follow up / Mortality Determination						X

Procedure

On the day of the procedure, the subject will be randomized into the HPI arm or the non-HPI arm (control group). If the subject is randomized into the HPI arm, the clinician will receive trial research nurse support and will use the Acumen™ HPI Software Feature with the Acumen IQ Sensor to monitor the subject. The initiation of HPI in the CVICU will not start until 15-30 minutes after the HPI arm subject arrives in the CVICU. Once HPI is initiated in the CVICU, HPI-based interventions will be held for at least 5 minutes before extubation and will also be held for at least another 5 minutes after extubation.

All subjects, regardless of randomization, will be equipped with an Acumen IQ Sensor. If the subject is not randomized into the HPI arm, the clinician will use non-protocolized standard of care.

7. STATISTICAL METHODS

Statistical Analysis Plan (SAP)

There will be a formal SAP, separate from this HPI CARE Trial protocol. The formal SAP will be completed prior to database lock and the analysis of any HPI CARE Trial endpoints data. The SAP will detail the planned statistical analyses. The subsections below summarize the planned analyses.

Primary Effectiveness Endpoint

The primary objective of this trial is to determine whether the use of the Acumen™ HPI Feature Software to guide hemodynamic management in critically ill patients in the cardiac operating room (OR) and the cardiovascular intensive care unit (CVICU) reduces the duration (t[mins]) of hypotension below a threshold of Mean Arterial Pressure (MAP), defined as MAP <65mmHg.

Sample Size Justification

In the HPI CARE Trial, the reduction of the mean duration of hypotension in the operating room (OR) and intensive care unit (ICU), is the primary endpoint. The following statistical hypotheses are designed and used for the sample size estimation.

$$H_n: \mu_1 \geq \mu_0$$

$$H_a: \mu_1 < \mu_0$$

where μ_1, μ_0 are the mean hypotension duration of the test arm and reference arm, respectively.

Because there are no publications available targeting hypotension management in the ICU, the sample size estimation is conducted based on the summary statistics from OR measurement. By the summary statistics (mean and standard deviation) of hypotension duration from post-CPB and closed chest ^[3,5], the following statistics are calculated and applied in sample size estimation: hypotension mean=29 (minutes), standard deviation=29.4 (minutes).

By clinical study design, type I error $\alpha = 0.025$ (one side test), test power= $(1 - \beta) = 0.80$, the expected hypotension duration reduction rate by HPI software and the treatment protocol is 30%, the expected ratio of hypotension duration standard deviation divided by the mean hypotension in the test arm will be 1.10 (obtained from a previous non-cardiac OR HPI study, Edwards Lifesciences), with SAS PROC POWER, the estimate of sample size is 171 per group. β is type II error.

Primary Safety Endpoint

The primary safety endpoint is to assess all serious intraoperative and post-operative adverse events through 30 days, including serious device-related events.

Analysis Populations

A. mITT population

The Modified intent-to-treat (mITT) population is composed of all subjects who pass the screen (inclusion/exclusion) evaluation, sign the informed consent form (ICF), are assigned a subject ID, and are randomized to a study group. This includes roll-in and pivotal subjects.

B. FAS population

FAS (full analysis set) population is composed of all pivotal subjects with valid HemoSphere observations.

C. PP population

The per protocol (PP) population is composed of all pivotal subjects without protocol deviations.

D. CC population

The complete cases (CC) population is composed of all the pivotal subjects who complete surgery and complete the trial.

Analysis Methods for the Primary Endpoint

The primary study objective is to evaluate if the use of HPI software in conjunction with a treatment protocol can statistically reduce the study patient's hypotension duration by the measurements taken in the cardiac OR and ICU, which has been shown to correlate with morbidity and mortality. By the hypotheses designed in sample size calculation, the following t statistics will be used to judge if the hypotension duration of the study arm with HPI software is statistically shorter or smaller than the control arm without HPI software.

$$t = \frac{\widehat{\mu}_1 - \widehat{\mu}_0}{\sqrt{S_p^2 \left(\frac{1}{n_1} + \frac{1}{n_0} \right)}}$$

Here $\widehat{\mu}_1, \widehat{\mu}_0$ is the mean hypotension duration estimation of the test arm and reference arm, respectively. The pooled variance, $S_p^2 = \frac{(n_1-1)*S_1^2 + (n_0-1)*S_0^2}{n_1+n_0-2}$, n_1, n_0 is the final valid subjects in test arm and reference arms respectively, S_1^2 and S_0^2 are the variance estimates of the test arm and reference arm respectively.

By the t statistics calculated with the data from clinical operation, compares to the critical t value ($t(\alpha', n_1 + n_2 - 2)$) to judge if null hypothesis is rejected. Here α' is the split type I error by study design for interim analysis and the final analysis, $n_1 + n_2 - 2$ is the degree of freedom.

For the interim analysis, by Pocock methodology with one-sided t test, $\alpha' = 0.015$. If p value deduces from the actual t value with $n_1 + n_2 - 2$ degrees of freedom is less than α' , H_0 will be rejected.

For the final analysis, using the Pocock methodology, with one-sided t test, $\alpha' = 0.015$. A similar computation will be done at the interim analysis.

All the other statistical methodology used in sensitivity analysis, safety analysis, and exploratory analysis will be detailed in the SAP.

Note: In this study, the sample size is not big enough to ignore the approximate property with Z score test, especially in the interim analysis.

Planned Interim Analyses

To monitor the effectiveness and safety of HPI software on hypotension management in cardiac surgery and ICU, one interim analysis is planned and will be conducted at the time that half of the enrolled study subjects complete surgery and the hemodynamic measurements are downloaded from the monitoring platform.

To compensate for the early look at the data during the interim analysis, using the Pocock methodology, for this study design, 11% extra study subjects will be enrolled. Considering drop-out through ICF withdrawal, subjects lost to follow-up, and roll-in subjects for training, another 10% attrition is added for subject enrollment; the final sample size is 175 subjects per group.

Secondary Endpoints

The following secondary endpoints will be analyzed per the SAP:

- TWA of MAP < 65 mmHg in the OR Period (T1)
- TWA of MAP < 65 mmHg in the CVICU Period (T2)
- TWA of MAP < 65 mmHg in the CVICU Period, pre extubation (T3)
- TWA of MAP < 65 mmHg in the CVICU Period, post extubation (T4)
- Mean duration in minutes of MAP < 65 mmHg in the time periods of T1, T2, T3 and T4
- Mean duration in minutes of MAP < 60 mmHg in the time periods of T1, T2, T3 and T4
- Mean duration in minutes of MAP < 55 mmHg in the time periods of T1, T2, T3 and T4
- Mean duration in minutes of MAP < 50 mmHg in the time periods of T1, T2, T3 and T4

Clinical endpoints:

- Acute kidney injury (AKI)⁷, as defined by the modified KDIGO criteria, stages 1, 2 and 3.
- Neurocognitive deficit, as evaluated by the MMSE, CAM-ICU 7, and bCAM assessments.
- Periprocedural Myocardial injury, measured with high-sensitivity Troponin I and as defined a threshold of 70 times the upper reference limit⁶. or >1400 pg/ml

THIS DOCUMENT CONTAINS CONFIDENTIAL AND PROPRIETARY INFORMATION OF EDWARDS LIFESCIENCES, LLC. IT MAY NOT BE REPRODUCED OR DISCLOSED WITHOUT PRIOR WRITTEN PERMISSION FROM EDWARDS LIFESCIENCES, LLC.

Edwards Lifesciences, Edwards, the stylized E logo, HemoSphere, Acumen IQ, Swan Ganz and ForeSight Elite are trademarks of Edwards Lifesciences Corporation.

Additional Evaluations

The following additional evaluations will be included and are considered exploratory:

- Subgroup analysis of primary and secondary endpoints by age stratification
- Subgroup analysis of primary and secondary endpoints by gender
- Subgroup analysis of primary and secondary endpoints by race
- Protocol adherence to HPI alert, as defined by >50% HPI alerts with documented intervention per the suggested treatment algorithm within a 5 minute timeframe
- Difference in time spent in hypertension defined as TWA of MAP>110, >120 and >130 mmHg post-cardiopulmonary bypass CPB) through the first 8-hour ICU period as compared with the control group.
- In-hospital mortality rate
- Incidence of cerebral desaturations defined as total time below 10% relative to baseline NIRS values.
- Percent of monitoring time with CO or CI within 10% relative to pre-induction baseline
- ICU Length of Stay
- Hospital Length of Stay
- Time to extubation
- SOFA scores
- New onset atrial fibrillation detected prior to ICU discharge

THIS DOCUMENT CONTAINS CONFIDENTIAL AND PROPRIETARY INFORMATION OF EDWARDS LIFESCIENCES, LLC. IT MAY NOT BE REPRODUCED OR DISCLOSED WITHOUT PRIOR WRITTEN PERMISSION FROM EDWARDS LIFESCIENCES, LLC.

Edwards Lifesciences, Edwards, the stylized E logo, HemoSphere, Acumen IQ, Swan Ganz and ForeSight Elite are trademarks of Edwards Lifesciences Corporation.

